## OMT Treatment

The OMT treatment will begin with a brief physical examination to identify somatic dysfunction in the lumbar, pelvic, sacral, and lower extremity body regions that the treating physician judges to be relevant to the individual participant's sacral asymmetry. OMT will be performed with the specific goal of improving sacral asymmetry by treating the sacrum and the surrounding regions (lumbar, pelvis, and lower extremities). The types of OMT techniques used will include muscle energy, articular, or high velocity-low amplitude (HVLA) as indicated by the physical findings and will be at the discretion of the treating physician. Additional techniques such as Still, counterstrain, facilitated positional release, balanced ligamentous tension, and cranial techniques may also be used at the discretion of the treating physician with the total treatment time not to exceed 20 minutes. To encourage participation in the proposed study, participants who are assigned to the control group will have an opportunity to receive OMT after the second ultrasound assessment.

## Preliminary Data

As part of a study investigating the feasibility of integrating ultrasound into an OMM curriculum, 247 students assessed the sacral base asymmetry of another student using US. They measured SPSIS and SSB on the right and left sides, then calculated the SSD as (SSB) - (SPSIS) = (SSD). The results are shown in Table 1. The calculated SSD demonstrated a wide range of depths (0 to 4.03 cm). The sacral sulcus depth difference (SSDD) between the right and left sides also demonstrated a wide range (-2.01 to 2.52 cm). Negative SSDD values indicated that the right sacral sulcus depth was shallower than the left and positive values indicate that the right sacral sulcus was deeper than the left, although these differences were not statistically significant.

Table 1: Student measurements of sacral base landmarks (N=247).

	Left SPSIS (cm)	Left SSB (cm)	Right SPSIS (cm)	Right SSB (cm)	Left SSD (cm)	Right SSD (cm)	SSDD (cm)
Maximum	6.33	8.24	4.94	8.29	3.65	4.03	2.52
Minimum	0.49	1.48	0.37	1.67	0.00	0.33	-2.01
Average	1.72	3.61	1.64	3.62	1.88	1.98	0.10
STDev	0.81	0.96	0.77	0.97	0.59	0.63	0.57

Abbreviations: SPSIS, distance from skin to posterior superior iliac spine (PSIS); SSB, distance from skin to sacral base (SSB); SSD, sacral sulci depth calculated as (SSB) - (SPSIS) = (SSD); SSDD, sacral sulcus depth difference between right and left SSD.

## Data analysis

Power calculations performed on preliminary SSDD data suggested that recruiting 38 participants would allow us to detect mean difference of  $\pm 0.5$  cm in the two treatment groups at pre-post treatment analysis at 0.05 significance level with 80% power. We plan to recruit 40 participants total (20 in each group). While the students, who collected the preliminary data, were not expert ultrasonographers, the quantity of data allows for an estimation of the likely range of measurements that will be seen in the proposed study. Descriptive statistics such as means, ranges, and standard deviations (SD) for continuous variables and frequency and percent will be used to summarize the categorical data. Two sample *t*-tests will be used to compare mean age and BMI across groups.

Correlations between BMI and US measurements will be calculated for each landmark (SPSIS, SSB, SSD). Absolute asymmetry between left and right landmark measurements will be calculated as follows:

$$\text{absolute asymmetry} = |\text{landmark}_{\text{left}} - \text{landmark}_{\text{right}}|$$

To determine if absolute asymmetry increased, decreased, or stayed the same after intervention, direction of change in asymmetry will be calculated as follows:

$$\begin{aligned}\text{direction of change in asymmetry} &= |2^{\text{nd}} \text{ US landmark}_{\text{left}} - 2^{\text{nd}} \text{ US landmark}_{\text{right}}| >, <, \text{ or} \\ &= |1^{\text{st}} \text{ US landmark}_{\text{left}} - 1^{\text{st}} \text{ US landmark}_{\text{right}}|\end{aligned}$$

To account for total change in measurements at both left and right landmarks between the first and second US measurements, total change in asymmetry between first and second US assessments will be calculated as follows:

$$\text{total change in asymmetry} = |(1^{\text{st}} \text{ US landmark}_{\text{left}} - 1^{\text{st}} \text{ US landmark}_{\text{right}}) - (2^{\text{nd}} \text{ US landmark}_{\text{left}} - 2^{\text{nd}} \text{ US landmark}_{\text{right}})|$$

The Fisher exact test is to be used to test associations between group and direction of change in asymmetry at each landmark. Multiple linear regression models will be built to compare mean absolute asymmetry for each landmark measured during the first US assessment between groups while controlling for demographic characteristics, date of last pain, and frequency of pain. Similar multiple linear regression models will be built to compare mean total change in asymmetry from first to second US assessment between groups for each landmark between groups.

Mean absolute asymmetry at the first and second US assessments and mean total change in asymmetry for seated control and OMT groups will be compared using a 2-sample t test. To compare qualitative palpitory assessment of SBP and SSD with quantitative US measurements, US measurement of landmark position will be first converted to a qualitative assessment as follows:

- right anterior SBP or deep SSD = right US measurement > left US measurement
- right posterior SBP or shallow SSD = right US measurement < left landmark measurement
- equal SBP or SSD = right US measurement = left US measurement

To compare agreement between qualitative palpitory and US assessments of SBP and SSD,  $\kappa$  and associated 95% CIs will be calculated. Values less than or equal to 0 indicated no agreement; 0.01 to 0.20, none to slight; 0.21 to 0.40, fair; 0.41 to 0.60, moderate; 0.61 to 0.80, substantial; and 0.81 to 1.00, almost perfect agreement.

To determine if US localization of landmarks at the sacral base was reliable, intraclass correlation coefficients (ICC) and associated 95% CIs will be calculated for US measurements from the first to second US assessment for each landmark. For ICC, 0.7 to 0.8 was considered good; 0.8 to 0.9, very good; and 0.9 to 1.0, excellent.  $P \leq 0.05$  was considered significant. Data analysis will be performed using SAS statistical software version 9.4 (SAS Institute, Inc.).

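### The only power figure (38 participants, 80% for ±0.5 cm) rests on the signed left-right difference SSDD, which no planned between-group test compares

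*Combined protocol and SAP*

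**What the plan says.** The combined protocol and SAP has one power statement, in Data analysis: "Power calculations performed on preliminary SSDD data suggested that recruiting 38 participants would allow us to detect mean difference of" ±0.5 cm between the two groups, "at pre-post treatment analysis at 0.05 significance level with 80% power". Recruitment is set at 40, 20 per group. The sentence prints no SD, test, sidedness or pre-post correlation.

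Preliminary Data explains the variable: "Negative SSDD values indicated that the right sacral sulcus depth was shallower than the left", and positive values mean the reverse. The difference "also demonstrated a wide range (-2.01 to 2.52 cm"). Table 1 gives it a mean of 0.10 and an SD of 0.57 cm (N=247).

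Data analysis plans these between-group ultrasound comparisons:

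- Two-sample t-tests: "Mean absolute asymmetry at the first and second US assessments and mean total change in asymmetry". Both quantities are defined as absolute values.
- Regression: absolute asymmetry at the first assessment, and "Similar multiple linear regression models will be built to compare mean total change in asymmetry from first to second US assessment between groups".
- Direction of change: "The Fisher exact test is to be used to test associations between group and direction of change in asymmetry at each landmark". The direction compares |L−R| at the two assessments.

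The right/left sign is used only in the kappa analysis against palpation, and the ICCs use the landmark measurements. Neither compares groups. Ultrasound Assessment says that measurements will be compared before and after, but names no test.

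**The concern.** The power figure and the tests are on different scales. Taking the absolute value changes the mean, the SD and the meaning of 0.5 cm. It also changes what OMT can move. OMT Treatment describes the aim as improving asymmetry, which pulls right-deep and left-deep participants in opposite directions. The signed group mean can then stay almost still while |L−R| falls substantially.

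At stake is the only justification given for the sample size. If the 80% belongs to no planned test, the plan does not say how likely any of its comparisons is to detect a given OMT effect.

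**Working it through.** **Inputs.** From Data analysis: difference 0.5 cm, alpha 0.05, power 80%, N 38 (40 recruited). From Table 1: SSDD mean 0.10, SD 0.57 cm. The tabulated mean is signed: right SSD 1.98 − left SSD 1.88 = 0.10.

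**1. The plan's own figure.** Normal approximation, two-sided:

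n per group = 2(z₀.₉₇₅ + z₀.₈₀)² SD²/δ² = 2 × 7.849 × 0.3249 / 0.25 = 20.4, so 21 per group, 42 in total.

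The noncentral t needs 22 per group, 44 in total. Power by t-test is 74.9% at 19 per group, 77.1% at 20 and 81.1% at 22. One-sided, the total is 34. None of these is 38.

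A change score has SD 0.57√(2(1−r)). At r = 0.55 this is 0.541, and n = 2 × 7.849 × 0.2924 / 0.25 = 18.4, so 19 per group, 38 in total. Across the normal and t versions, 38 needs r of about 0.53 to 0.58. A baseline-adjusted analysis with r of about 0.3 also gives 38. The plan states no such input.

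**2. Could absolute values have been used?** If SSDD is normal (0.10, 0.57), |SSDD| has mean 0.46 and SD 0.35 cm. Then n = 2 × 7.849 × 0.349² / 0.25 = 7.6, so 8 per group: 16 in total, or 18 by t. That is far from 38, so signed values are much the likelier source.

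**3. What 0.5 cm means on the tested scale.** Mean |SSDD| is about 0.46 cm under normality. Without any distributional assumption it cannot exceed √(0.10² + 0.57²) = 0.58 cm. A mean reduction of 0.5 cm in |L−R| is therefore about complete correction or more. Conversely, if OMT removed all asymmetry the signed mean would move only from 0.10 to 0, and a signed test at 20 per group would have 8–13% power (simulated as in step 4).

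**4. Power of two planned t-tests for SSD, 20 per group, two-sided 0.05.** Simulation with 20,000 trials per cell and normal values. The plan gives neither the reliability of the left-right difference nor the form of the OMT effect, so both are assumptions. Here reliability (or pre-post correlation) is 0.90:

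| Assumed OMT effect | Second-assessment \|L−R\| | Total change |
|---|---|---|
| Half of true asymmetry removed | 59% | 32% |
| Observed difference halved | 76% | 20% |
| All true asymmetry removed | 99% | 91% |
| Uniform +0.5 cm signed shift | 39% | >99% |

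With half of true asymmetry removed, moving reliability from 0.80 to 0.98 takes power from 44% to 73% for |L−R| and from 13% to 97% for total change. Table 1's extremes lie (2.52 − 0.10)/0.57 = 4.2 and (2.01 + 0.10)/0.57 = 3.7 SD from the mean, so heavier tails are plausible. With a t distribution on 5 df for the true values the ranges become 33–58% and 12–91%.

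Table 1 gives no left-right difference SD for SPSIS or SSB, so none of this extends to those landmarks.

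**The case against.** SSDD is the right source variable. For SSD, |L−R| is |SSDD| and total change is the absolute change in SSDD, so the gap is an unstated transformation and not an unrelated measure. That stands, but the transformation is exactly what changes the SD and the meaning of 0.5 cm.

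The plan prints neither SD nor test, so use of signed values is inferred. That also stands. The inference rests on the definition of SSDD, its only tabulated SD, and the 16 to 18 participants that the absolute scale would give.

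A reader might infer that 38 is an arithmetic error. The documents do not support this: the sentence refers to a pre-post analysis, a moderate correlation would yield 38, and 40 are recruited.

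A reader might also infer that a null result could not be interpreted. That goes too far. Interpretation rests mainly on the estimates and their precision. The plan does address reliability: "For ICC, 0.7 to 0.8 was considered good; 0.8 to 0.9, very good; and 0.9 to 1.0, excellent". Those ICCs concern single landmarks rather than the left-right difference, but the repeat measurements will allow reliability of the difference to be computed. One experienced examiner and marked skin (Potential Limitations) make high reliability possible.

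Finally, the simulated powers are driven mainly by assumed reliability and assumed effect form, not by Table 1. That is correct, and it is why they serve only as illustrations.

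**Conclusion.** The mismatch holds: no planned between-group test compares mean signed SSDD or its signed change, so the stated 80% describes none of them. The one inferential step is that the signed SSDD values were the input.

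The tempting stronger reading is that the trial is underpowered. The documents do not show this. Power on the planned scales may be above or below 80%, depending on the reliability of the left-right difference and on the size and form of the OMT effect. The 0.46 cm mean assumes normality and that the student values carry over to trial participants; the 0.58 cm bound needs only the latter.

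The difference between 38 and 42–44 is a secondary reporting gap: on SD 0.57 the signed comparison has 77% power at 20 per group.

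The point is worth correcting because it concerns the whole sample-size rationale, but it does not invalidate the design.

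**What to change.** Keep 40 participants and all outcomes and tests. Replace the power sentence with one computed for a named planned test on its own scale, for example the two-sample t-test of SSD absolute asymmetry at the second assessment, or of SSD total change. State:

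- the SD on that scale and the sidedness;
- the assumed reliability or pre-post correlation of the left-right difference;
- the target effect, in cm or as a fraction of asymmetry removed;
- a sensitivity range over reliability and over the form of the effect.

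The 247 existing records can supply the SD and shape of |SSDD|. Preliminary Data describes no repeat measurements, so reliability must be a declared assumption. The 13–97% and 44–73% ranges above should not be adopted as the protocol's figures: they hold only for proportional correction of true asymmetry. State that power for SPSIS and SSB was not computed, or compute it from their own left-right difference SDs.

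If the signed figure is kept, label it as not applying to the planned tests, and either state the pre-post correlation assumed or restate it as 77% at 20 per group on SD 0.57.

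The cost is one rewritten paragraph and a short simulation. The downside is that a single 80% becomes a range that depends on assumptions.

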### A. Specific Aims

The long term objective of this study is to establish objective measurements of musculoskeletal changes that occur in response to osteopathic manipulative treatment (OMT). Many patients who suffer from low back pain (LBP) receive OMT to the lumbar, pelvic, sacral, and lower extremity body regions that helps resolve or manage their pain. The indication for OMT in a patient suffering from LBP is the presence of somatic dysfunction found during the physical examination. Somatic dysfunction is diagnosed when one or more of the following physical findings are present: tenderness, asymmetry, restricted range of motion, and tissue texture abnormalities. OMT is performed to specifically target these physical findings, after which the patient is reassessed for a reduction or resolution of the findings. In the clinical setting the assessment and reassessment of somatic dysfunction is performed using palpatory examination. Because palpatory findings commonly demonstrate poor interexaminer reliability, the proposed study will use ultrasound to establish pre- and postOMT musculoskeletal measurements of the relative asymmetry between the participants' pelvic and sacral bony landmarks. The investigators will use a control group to compare the changes in the pre and post OMT measurements to participants who have not received OMT. If ultrasonography is able to detect a significant change in the relative asymmetry between the pelvis and sacrum, then ultrasound may be useful for assessing and quantifying outcomes for OMT in a variety of body regions such as spine, shoulders, and knees. To determine if ultrasound is a reliable objective measure to assess OMT outcomes in LBP patients the following specific aims are proposed:

- Determine if ultrasound measurements of sacral landmarks are stable over 30 minutes in untreated participants.
- Determine the extent to which OMT affects the relative asymmetry between the pelvic and sacral landmarks as measured by ultrasonography.
- Determine if ultrasound measurements of sacral base asymmetry agree with palpatory assessment.

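### The only regression on post-treatment data models total change in asymmetry, which cannot tell improvement from worsening, and no planned analysis combines direction, size and the first-scan value

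*Combined protocol and SAP*

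**What the plan says.** The Data analysis section defines three quantities for each landmark. Write L1, R1, L2 and R2 for the left and right measurements at the first and second scans.

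- Absolute asymmetry: |L − R| at a given scan.
- Direction of change: whether |L2 − R2| is greater than, less than or equal to |L1 − R1|. Its purpose is "To determine if absolute asymmetry increased, decreased, or stayed the same after intervention".
- Total change: |(L1 − R1) − (L2 − R2)|. Its purpose is "To account for total change in measurements at both left and right landmarks between the first and second US measurements".

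These feed the following between-group analyses.

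- One set of regressions has first-scan absolute asymmetry as outcome, which is a pre-treatment comparison.
- A second set has total change as outcome: "Similar multiple linear regression models will be built to compare mean total change in asymmetry from first to second US assessment between groups". I take its covariates to be those of the first set (demographics, date of last pain, frequency of pain), since the models are called similar. First-scan asymmetry is not among them.
- For direction: "The Fisher exact test is to be used to test associations between group and direction of change in asymmetry at each landmark".
- Two-sample t tests cover "Mean absolute asymmetry at the first and second US assessments and mean total change in asymmetry".

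No primary outcome is named. Aim 2 is "Determine the extent to which OMT affects the relative asymmetry between the pelvic and sacral landmarks as measured by ultrasonography", which specifies no direction. The OMT Treatment section does: "OMT will be performed with the specific goal of improving sacral asymmetry".

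**The concern.** The outer absolute value in total change removes the sign. A group difference on it shows that positions moved more in one arm, not that asymmetry fell. Since treatment is given to reduce asymmetry, readers will want to know whether it did, and the plan's only post-treatment regression cannot answer.

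The plan's two direction-aware analyses each leave something out. The Fisher test uses both scans but reduces each participant to a category. The second-scan t test keeps size but ignores the first scan. No planned analysis uses |L2 − R2| − |L1 − R1| as a measured quantity, and none adjusts |L2 − R2| for |L1 − R1|. With 40 participants, a real correction may be missed although the data that would show it have been collected.

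**Working it through.** **The plan's own figure.** The Data analysis section gives 38 participants for a difference of 0.5 cm "at 0.05 significance level with 80% power". With the Table 1 SSDD SD of 0.57 and a two-sided test, N per arm = 2(1.96 + 0.842)² × 0.57² / 0.5² = 20.4. That rounds up to 21, or 42 in total (44 with the t distribution). A one-sided test gives 34. The figure of 38 needs an SD of about 0.55 (normal) or 0.535 (t), or a pre-post correlation of about 0.55 (normal), none of which the documents state. The point below does not depend on this. The calculation is based on signed SSDD, a different variable from total change.

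**The formula by hand.** Let D = L − R.

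| D at scan 1 (cm) | D at scan 2 (cm) | Total change | Change in absolute asymmetry |
|---|---|---|---|
| 0.6 | 0.1 | 0.5 | −0.5 (better) |
| 0.6 | 1.1 | 0.5 | +0.5 (worse) |
| 0.25 | −0.25 | 0.5 | 0 (side reversed) |

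The equivalence also holds for whole distributions. Let T be the true first-scan difference and e1, e2 independent, equal-variance, symmetric errors. If OMT halves every T, D1 − D2 = 0.5T + e1 − e2. If OMT enlarges every T by 50%, D1 − D2 = −0.5T + e1 − e2. Because e1 − e2 is symmetric about zero, the absolute values have the same distribution. No sample size separates the two cases.

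**Simulation inputs.**

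- From the documents: 20 per arm; SSDD mean 0.10 and SD 0.57 cm (Table 1); significance level 0.05.
- Assumed: two-sided tests, and reliability (rel) of the left-right difference of 0.7, 0.8, 0.9 or 0.95.
- True SSDD ~ N(0.10, SD 0.57√rel), with independent error of SD 0.57√(1 − rel) at each scan: 0.31, 0.25, 0.18 and 0.13 cm.
- The OMT arm's true second-scan value is the first-scan value times 1 (no effect), 0.5, 1.5 or −1.
- 20,000 trials per setting, Monte Carlo standard error at most 0.4 points. Exact ties do not occur with continuous data, so Fisher compares decreased with increased. The planned covariates were not simulated.

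**OMT halves every asymmetry: percentage of trials significant.**

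| Analysis | rel 0.7 | 0.8 | 0.9 | 0.95 |
|---|---|---|---|---|
| Total change (planned; t test) | 8 | 13 | 32 | 67 |
| Fisher on direction (planned) | 8 | 13 | 26 | 44 |
| Second-scan absolute asymmetry, t test (planned) | 31 | 44 | 59 | 67 |
| Change in absolute asymmetry, unadjusted | 23 | 38 | 67 | 91 |
| Second-scan absolute asymmetry adjusted for first scan | 34 | 54 | 83 | 98 |

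The adjusted model gains 3, 10, 24 and 31 points over the planned second-scan t test. With reductions of 30% and 70% the gain ranges from about 2 to 43 points.

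**Other scenarios.**

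- Asymmetry 50% larger: total change again gives 8/13/32/67%. The adjusted model flags worsening in 30/42/68/90%.
- Complete side reversal, absolute asymmetry unchanged: total change rejects in 92/99/100/100%, the adjusted model in 5%.
- Extra random shift in the OMT arm only: with SD 0.1 to 0.2 cm, total change rejects in 5–6/5–8/6–15/8–34%. With SD 0.3 to 0.4 cm it rejects in 11–21/18–35/39–66/72–92%, while mean absolute asymmetry in that arm rises from 0.46 to 0.52–0.56 cm.
- No effect: every test rejects in about 5%, Fisher in about 2%.

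**The case against.** The strongest reply is that the plan does address direction. Under randomisation, the t test on second-scan absolute asymmetry is valid and keeps both direction and size, and the Fisher test adds the direction of change. Nothing in the plan says a larger total change will be read as improvement, and the aims ask about change rather than benefit. For a question about movement, detecting a side reversal is a correct result. All of this stands. The point is therefore about missing efficiency and about what total change can support, not about an invalid analysis.

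The gain is also uneven. At reliability 0.7 it is 3 points for a halving, and the documents give no reliability for the left-right difference. In a separate run with a 70% reduction and error SDs of 0.3, 0.2 and 0.1 cm, the adjusted model reached 58, 95 and 100% against 55, 87 and 98% for the t test, gains of 2 to 8 points. The size should therefore be quoted as a range. In every improvement setting examined, however, the adjusted model did at least slightly better than the t test.

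Uniform worsening, complete reversal and OMT-only random shift are illustrations, not predictions. Error equal in both arms creates no bias in total change, and the blinded single examiner and skin marks make unequal variability less likely. These scenarios show what the score cannot distinguish, not what will happen.

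Finally, the simulation used SSDD only and omitted the planned covariates, and the added model brings one more group comparison for each of the three landmarks. Both limits stand, but neither is a reason to leave out the first-scan value.

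**Conclusion.** The concern holds and should be fixed. That total change scores improvement and worsening alike follows from its formula and needs no simulation. That no planned analysis combines direction, size and first-scan value follows from the text. The cost in power is conditional: for a halving of asymmetry, the best planned direction-aware test falls 3 to 31 points short of the adjusted model across the assumed reliabilities of 0.7 to 0.95. Those figures assume normal SSDD with the Table 1 mean and SD, independent errors of equal size at both scans, a proportional effect and no other covariates. The Table 1 values come from student examiners, so spread and reliability in the trial may differ. Total change remains a legitimate measure of whether anything moved.

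**What to change.** Add to the Data analysis section, for each landmark, a linear regression of second-scan absolute asymmetry |L2 − R2| on group, first-scan absolute asymmetry |L1 − R1| and the covariates already planned (demographic characteristics, date of last pain, frequency of pain). Name it as the between-group model for the treatment effect and report the adjusted difference with its 95% CI. Keep the Fisher test and the second-scan t test as planned. Keep the total-change results too, and state that they describe any positional shift and are not evidence of improvement.

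The cost is a sentence or two of text, one model per landmark and one degree of freedom in each for the first-scan term. No new data, visits or participants are needed, and every planned analysis can still be reported.

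### No landmark, measure or test is named primary for the OMT effect, and six post-treatment group tests at an unadjusted P ≤ 0.05 carry about an 18–20% chance of a false difference

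*Combined protocol and SAP*

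**What the plan says.** Section C states the primary aim, the effect of OMT on sacral base asymmetry. The second specific aim in Section A asks how far OMT affects asymmetry between the pelvic and sacral landmarks. Under OMT Treatment, the goal of treatment is to improve sacral asymmetry.

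The Data analysis section lists three landmarks (SPSIS, SSB, SSD) and defines three asymmetry measures:
- absolute asymmetry, the size of the left-right difference at one scan;
- direction of change, introduced by "To determine if absolute asymmetry increased, decreased, or stayed the same after intervention";
- total change, the absolute value of the difference between the signed left-right differences at the two scans.

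The post-treatment group comparisons are:
- "The Fisher exact test is to be used to test associations between group and direction of change in asymmetry at each landmark";
- regression: "models will be built to compare mean total change in asymmetry from first to second US assessment between groups for each landmark";
- t tests on absolute asymmetry at each scan, and "mean total change in asymmetry for seated control and OMT groups will be compared using a 2-sample t test". This sentence does not name landmarks.

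One threshold covers all of them: P ≤ 0.05 "was considered significant. Data analysis will be performed using SAS statistical software version 9.4". No comparison is called primary, and no order of testing or adjustment is given.

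On sample size: "Power calculations performed on preliminary SSDD data suggested that recruiting 38 participants would allow us to detect mean difference of" ±0.5 cm, at 0.05 and 80% power, with 40 to be recruited. Preliminary Data defines SSDD as a signed quantity: negative when the right sulcus is shallower than the left, positive when it is deeper.

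**The concern.** The plan has a primary aim but no rule for deciding whether it has been met. A reader cannot tell which of the group comparisons, or how many of them, would establish an OMT effect. The deciding result could be picked after the data are seen, and the 5% error rate that applies to each test does not apply to the conclusion.

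The measures also answer different questions. Direction of change and second-scan absolute asymmetry can show improvement. Total change cannot, because it drops the sign, yet it is given both a regression and a t test. A significant total-change result could be read as success even if asymmetry had grown.

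Finally, the ±0.5 cm in the power statement refers to a signed difference. It does not tell the reader what effect 40 participants can detect on any measure that the groups will be compared on.

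**Working it through.** **1. Count the tests.** Only post-treatment comparisons stated for each landmark are counted: Fisher on direction (3) plus regression on total change (3) = 6. First-scan comparisons are left out because they cannot show an OMT effect.

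**2. The plan's own figure.** Table 1 gives an SSDD SD of 0.57 cm. For a two-sided 0.05 test with 80% power, n per group = 2 × (1.960 + 0.842)² × 0.57² / 0.5² = 2 × 7.85 × 0.3249 / 0.25 = 20.4. That rounds up to 21 per group, 42 in total (44 with the t distribution). The stated 38 would need an SD of about 0.55: 2 × 7.85 × 0.3025 / 0.25 = 19.0 per group. The plan does not give the SD it used. This gap is a separate matter; what counts here is that the calculation is on the signed SSDD scale.

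**3. Reference value.** Six independent tests, each at exactly 0.05, would give 1 − 0.95⁶ = 26.5%. The true figure is lower for two reasons. Fisher's test is conservative at this size, and SSD is computed as SSB − SPSIS, so the landmarks are linked.

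**4. Simulation with no OMT effect.** There were 20 participants per group, with 10,000 trials in each of 16 settings. Left-right differences at SPSIS and SSB were normal, set so that the SSD difference has the Table 1 mean of 0.10 and SD of 0.57. Their correlation was varied from 0 to 0.79, and scan-to-scan reliability of the left-right difference from 0.31 to 0.90. Both are assumptions, because the documents do not give them. The regression used five covariates unrelated to outcome.

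| Tests at P ≤ 0.05 | Chance of at least one significant result |
|---|---|
| Three Fisher tests | 0.055–0.062 |
| Three total-change regressions | 0.132–0.142 |
| All six | 0.183–0.195 |
| SSD only: Fisher and regression | 0.066–0.075 |
| SSD only: these two plus two t tests | 0.122–0.135 |
| Twelve: the six plus both t tests at every landmark | 0.312–0.340 |

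**5. Effect of reading precision.** Separate runs of 8,000 trials in three settings rounded the readings, with a t test on total change in place of the regression (elsewhere the two gave almost the same rates). Rounding to 0.01 cm, as in Table 1, gave 0.178–0.202 for the six tests. Rounding to 0.1 cm gave 0.206–0.234. With 0.1 cm readings the unchanged category becomes common, and the size of each Fisher test rises from about 0.026 to about 0.044.

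**6. What total change measures.** With the same side larger throughout, a left-right difference going from 0.4 to 0.0 cm scores |0.4 − 0.0| = 0.4, and one going from 0.4 to 0.8 cm scores |0.4 − 0.8| = 0.4. For SSD, total change equals |SSDD at scan 1 − SSDD at scan 2|. It is therefore the closest planned counterpart of the power variable, but with the sign removed.

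**7. With the fix.** A single prespecified test of second-scan absolute SSD asymmetry, adjusted for the first scan, gave 0.046–0.053. A single SSD total-change test gave 0.047–0.050. Keeping all six tests at 0.05/6 = 0.0083 gave 0.029–0.043 overall.

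**The case against.** The best defence is that SSD is primary in all but name. Power was computed on SSDD, the power sentence refers to a pre-post analysis, and SSD total change is the absolute pre-post change in SSDD. That link is real. But the plan never calls SSD primary, and choosing SSD alone does not settle the measure or the test. About 7% remains over its Fisher test and regression, and about 13% if its two t tests are added.

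A second defence is that this is a small exploratory study. The protocol, however, calls it a prospective randomized controlled trial and gives a powered comparison at 0.05. If the intent is exploratory, the plan should say so and report estimates.

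A third is that total change is legitimate for the second aim, which asks whether asymmetry is affected, and that the plan pairs it with a direction measure. Both points stand. The weakness is the missing priority, not the presence of total change.

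The correlations and reliabilities in the simulation are assumed, but the six-test figure hardly moves across them.

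**Conclusion.** The point holds. With no OMT effect, the six tests stated at each landmark give about an 18–20% chance of at least one significant group difference, and about 21–23% if readings are to 0.1 cm. This assumes 20 analysed per group, no effect at any landmark, and the correlations and reliabilities listed above. With fine readings, most of the excess over 5% comes from total change.

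Three stronger readings are not supported:
- **That the rate is 31–34%.** This requires the t tests on total change and second-scan absolute asymmetry to be run at every landmark, which the plan does not state. It also counts total change twice.
- **That a false claim of improvement is inflated to the same degree.** The only measure stated for each landmark that can show improvement is direction. A significant Fisher result favouring OMT at any of the three landmarks occurred in about 2.3–3.6% of null trials, close to the 2.5% of a single two-sided test in one direction.
- **That only a very large reduction in absolute asymmetry is detectable.** If the student SSDD distribution applied, absolute SSD asymmetry would have mean about 0.46 and SD about 0.35 cm. Holding that SD fixed in both groups suggests that a reduction of about 69% is needed. But the SD shrinks with the mean: under proportional shrinkage, a 69% reduction has about 99% power, and 80% power is reached near 52% (0.24 cm). Scan error then pulls the other way. If reliability of the left-right difference is 0.31 or 0.54, removing all true asymmetry lowers the observed mean by only about 0.08 or 0.15 cm. The documents do not give that reliability, and they caution on the source: "While the students, who collected the preliminary data, were not expert ultrasonographers". No detectable difference can be fixed from them.

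**What to change.** Before analysis, add to the Data analysis section:
- One landmark, one asymmetry measure and one test as primary, at two-sided 0.05. An example is second-scan absolute SSD asymmetry compared between groups, adjusted for first-scan absolute SSD asymmetry and sex. The sponsor may prefer another landmark or measure; what matters is that it is a single choice made in advance.
- A statement that all other group comparisons are secondary, reported as estimates with 95% confidence intervals or Holm-adjusted, and not sufficient alone to claim an OMT effect.
- A statement that total change describes the size of change, not improvement.
- A restated detectable difference for 20 per group on the chosen scale, giving the assumed SD and reliability. If the scale is absolute asymmetry, the model should let the SD shrink with the mean and should include scan error.

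The cost is a few sentences and a revised power statement, with no new data. The downside is that a lone significant secondary result can no longer carry the conclusion, and the restated detectable effect may look less favourable than ±0.5 cm does now.
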